# 1 Background and Rationale

## 1.1. Background

In 2018, 4,655 people were diagnosed with tuberculosis (TB) in the UK, equivalent to a rate of TB of 8.3 per 100,000 population. This was the lowest recorded rate of TB in the UK for the last 10 years. People born outside the UK accounted for 72% of notifications in 2018. The proportion of people with drug-sensitive TB who completed treatment by 12 months was 84.7% in 2017; in addition, 5.3% died and 4.2% were lost to follow up. Only 2.7% of people with TB were coinfected with HIV in 2018; most (81.7%) were born outside the UK. Early data from 2019 suggests that the rate of TB may be higher in 2019 compared to 2018.

The standard treatment of drug-sensitive TB involves a 4-drug combination of anti-TB therapy (ATT) for 2 months (intensive phase of treatment), followed by a 2-drug combination for 4 months (continuation phase of treatment), making a total treatment duration of 6 months. Cure rates are around 97%.9

Drug-induced liver injury (DILI) is the commonest serious adverse effect of ATT. DILI may result from direct toxicity of the primary compound or an immunological response to one or more of the drugs. Unpredictable or idiosyncratic reactions which develop acutely account for most types of DILI. These reactions are unpredictable based on the pharmacological action of the drug, independent of drug dose and are relatively unusual for each drug.

Among those who develop DILI on ATT, 16% develop jaundice and 5.3% acute liver failure; the latter is the most severe outcome of DILI, of which 22% can be fatal. Most patients with DILI who report symptoms experience nausea, vomiting, anorexia and lethargy. Early detection of DILI with cessation of the inciting drug(s) serves to limit the severity of DILI and its consequences. Not all asymptomatic increases in liver enzymes while on ATT constitute DILI episodes. Some of the increase in liver enzymes are self-limiting or are attenuated through a process called hepatic adaptation (please see later). However, very high levels of liver enzymes (>5x upper limit of normal) in the absence of symptoms are thought to represent early DILI episodes that, if left untreated (ie. continued exposure to the inciting drug(s)), would progress to symptomatic DILI.

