Apart from any symptoms and sequelae related to DILI, a patient who experiences a DILI episode also suffers delay in the treatment of their primary illness. When a patient with active TB has a DILI episode, the overarching strategy is to i) stop the inciting drug(s), ii) allow the liver to recover and then iii) reintroduce as many first-line ATT drugs as possible to enable the highest chance of clinical cure of TB disease in the shortest length of time. The median duration of cessation of ATT is 18 days while reintroduction of ATT drugs takes a further 10 -14 days (median).2,12 Therefore, for each episode of DILI, a total of 28 days' delay can be expected before full ATT is re-started.12

Guiding the patient through recovery from DILI and re-establishment of ATT requires additional healthcare resources. In one study from Canada, 29 of 37 patients who developed serious ATT-related side effects made a total of 91 extra clinic visits, and the TB clinic nurses made an additional 30 home visits to 8 of these patients. If full standard first-line ATT is not reintroduced following DILI, modified regimens may require extension of the treatment duration beyond 6 months to achieve acceptable rates of clinical cure. This adds to patient and healthcare costs.

Trial	TB-DILI Trial	Protocol	1.2	date:	02-Aug-2022	Page 16 of 58
name:		version:				

Globally, rates of DILI following TB therapy of 2 - 25% are reported .14-18 In 2 UK studies, DILI was reported in about 7% of persons treated for TB; however, the definition of DILI differed between these studies.12,19

Roughly 53 - 57% of DILI episodes occur during the first 2 weeks of ATT, and 75 - 88% within the first 8 weeks, corresponding to the intensive phase of ATT.12,19-21

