# 1.2. Trial Rationale

In the National Health Service (NHS), the management of ATT-induced DILI is informed by both the NICE TB Guideline and the American Thoracic Society TB Guideline.8,9

The NICE TB Guideline (2016), section 1.7.4.1, recommends clinicians "sequentially reintroduce each of the anti-TB drugs at full dose over a period of no more than 10 days, starting with ethambutol and either isoniazid (with pyridoxine) or rifampicin." The NICE Guideline Development Group (GDG) acknowledged that the evidence supporting this recommendation was of very low quality; based on 2 trials (Sharma *et al.*, 2010, and Tahaoglu *et al.*, 2001). The recommendation was mainly developed by expert consensus.

The American TB Guideline (2006) also recommends sequential reintroduction of ATT; beginning with rifampicin (with or without ethambutol), then adding isoniazid after 3 to 7 days. In addition, it recommends *"For those who have experienced prolonged or severe hepatotoxicity, but tolerate reintroduction with rifampicin and isoniazid, rechallenge with pyrazinamide may be hazardous. In this circumstance, pyrazinamide may be permanently discontinued, with treatment extended to 9 months.* 

Trial	TB-DILI Trial	Protocol	1.2	date:	02-Aug-2022	Page 18 of 58
name:		version:				

Although pyrazinamide can be reintroduced in some milder cases of hepatotoxicity, the benefit of a shorter treatment course likely does not outweigh the risk of severe hepatotoxicity from pyrazinamide rechallenge."

These two Guidelines are interpreted variously by clinicians, in the NHS and globally, resulting in a range of clinical practice. Some clinicians prefer to routinely avoid reintroducing pyrazinamide (Z), aiming instead for a 9-month non-Z containing regimen. Others consider the severity of DILI in deciding on reintroduction of Z; however, the threshold for classifying 'milder DILI' also varies. It is equally difficult for patients to make informed choices. There are no data on patient-related costs or quality of life (QoL) measures to inform the balance between risk of recurrent DILI versus extension of treatment duration.

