# 8. Trial procedures and assessments

#### 8.1. Summary of assessments

A summary of trial procedures is shown in figure 2. A detailed description of each procedure can be found in section 8.2.

Figure 2: Summary of trial procedures time point

Trial	TB-DILI Trial	Protocol	1.2	date:	02-Aug-2022	Page 30 of 58
name:		version:				

															TRIAI	L PERI	OD						
TIMEPOINTS	E	R	Pha	ise A						Pha	se B				Phase	e C		DIL	Recurrence		ЕоТ		Follow- up Post R
Timepoint [Weeks]	W-2	W-1				W0				W1	W2	W4	W6	W8	W16	W24	W32	Diagnosis	2-Weeks after	W25	W33	*	W52
Timepoint [Days]		-1	0	1	3	4	6	7	9									of DILI	treatment re-start				
Tolerance [Days]	а	±2	±1	±1	±1	±1	±1	±1	±1	±4	±4	±4	±4	±4	±14	±14	±14	-	-	-	-		-
ENROLMENT:																							
Eligibility screen	Х																						
Informed consent	Х																						
Baseline Assessments																							
Adjudication panel confirmation	Х																	Х					
EQ-5D-5L	Х																						
Randomisation		Х																					
CONTROL ARM																							
Drug Re-Introdcution																							
Reintroduce EH				Х																			
Reintroduce R						Х																	
Reintroduce Z								Х															
Drug Discontinuation																							
Discontinue Z+R														Х									
Assessments																							
LFT (suggested not mandated)			х		х		х		х	х	х	x	x	x	x	x	x	х	х				
EQ-5D-5L			Х								Х							Х	Х	Х			Х
Follow-Up post EoT																							
Follow-up telephone call																				Х		Х	
INTERVENTION ARM																							
Drug Re-Introdcution																							
Reintroduce EH				Х																			
Reintroduce R						Х																	
Drug Discontinuation																							
Discontinue R														Х									
Assessments																							
EQ.5D-5L			Х						_	Γ.	Х							Х	Х		Х		Х
Follow-Up post EoT						CI 31				_					 								
Follow-up telephone call					ľ	5.510	[														Х	Х	

E = Enrolment

R = Randomisation

EoT = End of Treatment

a. The enrolment period will occur at the onset of DILI, the period between E & R will be variable dependent upon patient recovery. Predicted average time is 2 weeks

\* Every 12 weeks after EoT until 12 months post R

Trial	TB-DILI Trial	Protocol	1.2	date:	02-Aug-2022	Page 32 of 58
name:		version:				

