#### Phase B

- EQ-5D-5L completion at W2 for both arms
  - Discontinuation of Drug(s) at W8:
    - Control Arm: E and Z
      - o Intervention Arm: E

Trial	TB-DILI Trial	Protocol	1.2	date:	02-Aug-2022	Page 33 of 58
name:		version:				

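### Figure 2 and section 9.1.4 of the protocol disagree, in both arms, on which drugs stop at week 8

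*Protocol*

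**What the plan says.** Two places in protocol version 1.2 say what stops at week 8.

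- **Figure 2 (section 8.1).** The control arm row reads "Discontinue Z+R" and the intervention arm row reads "Discontinue R". The mark in each row falls in the W8 column.
- **Section 9.1.4, Phase B.** Under drug discontinuation at W8 it gives "Control Arm: E and Z" and "Intervention Arm: E".

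Other text bears on the question without settling it. Section 1.1 describes the standard continuation phase as two drugs for four months and does not name them. Section 1.2 reports the American guideline on reintroduction as "beginning with rifampicin (with or without ethambutol), then adding isoniazid after 3 to 7 days". For patients who tolerate rifampicin and isoniazid after prolonged or severe hepatotoxicity, it adds that "pyrazinamide may be permanently discontinued, with treatment extended to 9 months". Section 7.1 refers to the NICE and ATS guidelines for formulation and dose and does not mention the week-8 stop.

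The end-of-treatment contact for the intervention arm also differs: W33 in Figure 2, W37 in section 9.1.4.

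**The concern.** Which drugs a participant takes after week 8 is a core treatment instruction, and the protocol gives two incompatible answers in each arm. Figure 2 is the schedule that staff are likely to consult at a glance; section 9.1.4 is the prescribing text. A site that worked from the figure would stop rifampicin and continue ethambutol, while a site that worked from section 9.1.4 would do the reverse.

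Record keeping is exposed too. Section 7.3 puts medication start and stop dates in the eCRF, and section 9.5 assesses compliance centrally from eCRF data. With two schedules in force, the same week-8 stop could be read as compliant or as a deviation.

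**Working it through.** **1. Is R rifampicin in Figure 2?** The legend also uses E for enrolment and R for randomisation, but those explain column headings. The disputed rows sit under the drug headings, next to rows that reintroduce EH, R and Z, so R there is rifampicin. Two separate rows carry the same swap, which makes a PDF reading error unlikely.

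**2. What remains after week 8**

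| Arm | Starts with | Figure 2 stops | Leaves | Section 9.1.4 stops | Leaves |
|---|---|---|---|---|---|
| Control | E, H, R, Z | Z, R | E + H | E, Z | H + R |
| Intervention | E, H, R | R | E + H | E | H + R |

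The two sources agree only that pyrazinamide stops in control. They disagree in both arms on whether ethambutol or rifampicin stops.

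**3. Worst-case exposure after randomisation at a site following Figure 2.** Inputs: rifampicin restarts on day 4 (Figure 2) and W8 is day 56. Section 9.1.4 places the end-of-treatment contact one week after treatment ends, at W25 (control) and W37 (intervention), so treatment ends at W24 (day 168) and W36 (day 252).

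- Rifampicin under Figure 2: 56 − 4 = 52 days in either arm.
- Rifampicin under section 9.1.4: control 168 − 4 = 164 days; intervention 252 − 4 = 248 days.
- Ratios: 52/164 = 32%; 52/248 = 21%.
- Extra ethambutol under Figure 2: control 24 − 8 = 16 weeks; intervention 36 − 8 = 28 weeks.

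The intervention figures combine the stop in Figure 2 with the course length in section 9.1.4. If Figure 2's W33 contact were used instead, treatment would end at W32 (day 224). The comparison would then be 52 against 224 − 4 = 220 days (24%), with 32 − 8 = 24 extra weeks of ethambutol. All these counts exclude doses taken before the first DILI episode, so the percentages are not shares of the whole TB course.

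**4. How much of the risk period is in dispute.** Section 1.1 puts DILI episodes on initial treatment at "75 - 88% within the first 8 weeks, corresponding to the intensive phase of ATT". If recurrences followed the same timing, which is an assumption, 100 − 88 = 12% to 100 − 75 = 25% would fall after week 8.

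**5. W33 or W37.** Section 1.2.3 gives 9 months against 6. Control treatment lasts 24 weeks, so scaling gives 24 × 9/6 = 36 weeks and a contact at W37. In calendar months, 9 months is 39.1 weeks and the contact would be at W40.1, which is 3.1 weeks from W37 and 7.1 weeks from W33. W37 is the closer on either convention, though exact only on the first.

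**The case against.** The strongest reply is that few prescribers would act on the figure. Section 8.1 presents it as a summary and sends the reader elsewhere for detail. Section 9.1.4 carries the prescribing heading. Section 7.1 ties the arms to the NICE and ATS guidelines, both regimens are described as standard care, and the sites are NHS TB centres. This stands as an argument about likelihood. It does not remove the conflict, because nothing in the protocol says which text governs the week-8 stop.

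A reader might infer more than the documents support:

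- **Harm from ethambutol plus isoniazid.** No section says that this pair is less effective or less safe in continuation than isoniazid plus rifampicin. Section 1.1 says that ethambutol very rarely causes DILI and counts rifampicin among the drugs of concern. A claim of lost efficacy would rest on outside knowledge.
- **Bias in the trial result.** The same drugs are swapped in both arms, and most initial DILI episodes come before week 8. The swap would last longer in the intervention arm because its course is longer, but the protocol gives no basis for turning that into an effect on the comparison.
- **An instruction to stop intervention treatment at W32.** No text says so. Sections 9.1.4 and 15 tie the contact to the actual end of treatment.
- **Participants already treated per Figure 2.** Nothing shows this.

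**Conclusion.** The contradiction is real, sits in current text and affects both arms. Section 9.1.4 is probably the intended version: it is the prescribing section, and the guideline text in section 1.2 turns on tolerating rifampicin and isoniazid. That is an inference, since the continuation pair is named nowhere else in the readable text; the trial flow diagram was not legible in the copy available.

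The finding is an ambiguous treatment instruction that changes which drug is taken after week 8. Its size, 52 days of rifampicin against 164 or 248, is a post-randomisation worst case for a site that took the stop from Figure 2 and the course length from section 9.1.4. No effect is shown on the comparison with and without pyrazinamide, the sample size or the primary endpoint. The difference of 37 − 33 = 4 weeks in the intervention end-of-treatment contact is a minor companion error.

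**What to change.** After confirmation by the clinical leads:

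- in Figure 2, change the control row to *Discontinue E+Z* and the intervention row to *Discontinue E*;
- change the intervention end-of-treatment column from W33 to W37, to match section 9.1.4;
- issue the corrected schedule to all sites.

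This alters three entries in one figure. It needs no new data and no change to sample size or analysis. The downside is a possible protocol amendment, since section 17 has the protocol approved by the MHRA and REC.

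Purely editorial, in the same revision: sections 6.1 and 8.1 refer to a section 8.2 that does not exist (the material is in section 9), and Appendix A cites sections 9 and 10 for adverse event reporting and data handling, which are sections 10 and 11.

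### Figure 2 and section 9.1.4 of the Protocol stop different drugs at week 8: rifampicin in the figure, ethambutol in the text, in both arms

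*Protocol*

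**What the plan says.** The control regimen is ethambutol, isoniazid, rifampicin and pyrazinamide (EHRZ). The intervention regimen is the same without pyrazinamide (EHR). Both are stepped down at week 8 (W8), and the Protocol gives that step twice.

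- **Section 8.1, Figure 2, drug discontinuation rows, W8 column.** Control: "Discontinue Z+R". Intervention: "Discontinue R".
- **Section 9.1.4, Phase B, drugs to stop at W8.** "Control Arm: E and Z" and "Intervention Arm: E".

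Section 8.1 introduces the figure as a summary and says of the detail: "A detailed description of each procedure can be found in section 8.2". The Protocol has no section 8.2. The figure's legend gives "R = Randomisation" and uses E for enrolment, although the same letters stand for drugs in the figure's rows.

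Section 1.1 says that standard treatment continues with two drugs after the intensive phase but does not name them. Section 7.1 refers to the NICE and ATS guidelines for formulation and dose, and does not list the continuation drugs either.

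**The concern.** The two places describe the same step, in the same week and the same arms, and give incompatible instructions on which anti-tuberculosis drug to withdraw. A schedule table is a natural working reference for site staff. A site that follows Figure 2 would take participants off rifampicin and keep them on ethambutol for the rest of the course. A site that follows section 9.1.4 would do the reverse. Whatever a site does, it departs from one of the two statements, so central checks of protocol compliance (section 9.5) have no single standard to check against.

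The choice bears on the trial's subject. Section 1.1 lists rifampicin among the drugs of concern for drug-induced liver injury (DILI) and says that ethambutol very rarely causes it. The two versions therefore imply different hepatotoxic exposure after week 8, while DILI recurrence, the primary outcome, is still being counted.

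**Working it through.** **Is it really week 8, and really rifampicin?** Counting the columns of Figure 2 from the row label puts the mark in both discontinuation rows in the 14th column, which is W8 in the header row. The letter R appears in both arms' discontinuation rows. The same table also has rows that reintroduce R, and E together with H, in both arms. In these rows the letters can only mean drugs, despite the legend. A misread of the PDF is unlikely, since R stands in two separate rows.

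**What remains after week 8.** Subtract the stopped drugs from each regimen:

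| Arm | Regimen | Figure 2 stops | Figure 2 leaves | 9.1.4 stops | 9.1.4 leaves |
|---|---|---|---|---|---|
| Control | E, H, R, Z | Z, R | E, H | E, Z | H, R |
| Intervention | E, H, R | R | E, H | E | H, R |

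Both versions stop pyrazinamide in control, and both keep isoniazid in each arm. Only the second continuation drug is in conflict.

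**Which version is likelier?** The Trial Summary ties the intervention to the ATS guideline. The guideline text quoted in section 1.2 concerns patients who "tolerate reintroduction with rifampicin and isoniazid", for whom "pyrazinamide may be permanently discontinued, with treatment extended to 9 months". That fits a course carried by isoniazid and rifampicin, as in section 9.1.4. It does not say that ethambutol stops at week 8, and it does not name the control arm's continuation drugs. So section 9.1.4 is the probable intention, but this is inferred.

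**Time on the wrong second drug for a participant treated by Figure 2.** Section 9.1.4 places the end-of-treatment questionnaire one week after treatment ends, at W25 (control) and W37 (intervention), so treatment ends at W24 and W36. Figure 2 shows W33 for the intervention arm, so W32; that difference is a separate inconsistency.

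- Control: (24 − 8)/24 = 16/24 = 67%.
- Intervention: (36 − 8)/36 = 28/36 = 78%, or (32 − 8)/32 = 24/32 = 75%.

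**Participants who could meet the instruction.** Section 14.1.1 assumes 157 analysable per arm out of 175, with recurrence of 10% and 1.5%. If every assumed loss and every recurrence came before week 8:

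157 × 0.90 + 157 × 0.985 = 141.3 + 154.6 = 295.9, about 296 of 350 (85%).

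The ceiling is 350. The lower figure ignores stops for other reasons.

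**Primary-outcome events after week 8.** Section 1.1 puts 75% to 88% of initial DILI within the first 8 weeks. If recurrences on re-treatment followed the same timing (an assumption), 12% to 25% would fall after week 8.

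- Control: 157 × 0.10 = 15.7 expected; × 0.12 to 0.25 = 1.9 to 3.9.
- Intervention: 157 × 0.015 = 2.4 expected; × 0.12 to 0.25 = 0.3 to 0.6.

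**The case against.** The best case on the other side accepts the conflict and disputes its weight.

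- **The figure is only a summary.** Section 8.1 defers to a detailed description elsewhere. Section 6.1 also cites section 8.2, for baseline data, and that content sits in section 9.1.2. Section 9 is evidently the detailed text, and an ordinary reading would let it prevail. This is fair, and it supports section 9.1.4 as the intended version. It is still something a site has to work out, from a cross-reference that leads nowhere.
- **Sites would probably not follow the figure.** Treatment is given in NHS TB centres, both regimens are accepted standard care, and section 7.1 points to national guidelines. The chance of literal compliance may well be low. The percentages of treatment time apply only to participants whose site does follow the figure, and the 296 to 350 are those who could reach the step, not those likely to be affected.
- **The primary comparison is little affected.** Both arms end on the same pair of drugs under either version. Putting ethambutol in place of rifampicin would, if anything, lower exposure to a drug of hepatotoxic concern. This stands.
- **An effect on cure is not shown.** The remark in section 1.1 about longer treatment for modified regimens concerns incomplete reintroduction after DILI. It does not address the second drug after week 8. An effect on clinical cure, a secondary outcome, is plausible, but the Protocol gives no figure for it and the point carries little weight here.

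None of this removes the contradiction. An instruction on which drug to withdraw should not depend on sites noticing that one of its two statements is wrong.

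**Conclusion.** The contradiction is real and must be corrected. At week 8 Figure 2 leaves both arms on ethambutol and isoniazid, and section 9.1.4 leaves both on isoniazid and rifampicin. Section 9.1.4 is the likelier intention, subject to clinical confirmation.

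The rating rests on the kind of error: an operative drug-stopping instruction, given in two incompatible forms in both arms, with no stated precedence. For a participant treated by the figure it governs two thirds to just over three quarters of the treatment course. The effect on the primary comparison is limited: about 2 to 4 control recurrences and fewer than one intervention recurrence after week 8, if recurrence follows the timing of initial DILI. The comparison of regimens with and without pyrazinamide, the pilot's definition of adherence (section 7.5.2) and the sample size are not undermined.

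**What to change.** 1. Have the clinical lead confirm the continuation drugs for each arm.
2. If section 9.1.4 is confirmed, change the W8 rows of Figure 2 to stop ethambutol and pyrazinamide in control and ethambutol in intervention. Write the drug names in full, because the legend uses E and R for enrolment and randomisation.
3. Name the continuation-phase drugs (isoniazid and rifampicin, if confirmed) for each arm in section 7.1.
4. Redirect the section 8.2 reference in section 8.1 to section 9.
5. Send sites a clarification letter, and check prescribing after week 8 at any open sites.

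The cost is two table rows, one line in section 7.1 and one cross-reference in the next amendment, plus the letter and the prescribing check. Sample size, randomisation and data collection are unaffected.

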## 2.2. Objectives and outcome measures

#### 2.2.1. Primary

• DILI recurrence within 12 months following randomisation.

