# 4.2. Exclusion Criteria

- Requirement for alternative ATT
- Unable to provide written informed consent

To obtain a realistic estimate of safety and tolerability, no adult will be excluded on the basis of (older) age, liver disease, alcohol use, HIV status or other medication use.

The NICE TB Guideline does not outline a specific LFT monitoring plan. Participating sites will be encouraged to adopt a preferred monitoring plan with flexibility for local practice variations across hospitals. Sites will be requested to upload all LFTs performed onto the eCRF.

**Definition of DILI**. This will be based on internationally recognised criteria that take into account baseline measurements.

Table 1. Clinical chemistry criteria for DILI in those with normal liver enzymes at baseline.

Any one of the following-

- >3-fold elevation in ALT and either bilirubin elevation exceeding 2 x upper limit of normal (ULN) or presence of hepatitis symptoms (anorexia, nausea, vomiting, abdominal pain)
- >5-fold elevation above ULN of alanine aminotransferase (ALT)
- >2-fold elevation above the ULN for alkaline phosphatase (ALP), particularly with accompanying 5'-nucleotidase or gamma-glutamyl transpeptidase (GGT) elevations and when there is no known bone pathology driving the rise in ALP.

Isolated hyperbilirubinemia or raised GGT in the absence of other liver enzyme elevations will not qualify as DILI. These case definitions are in agreement with those from the American Thoracic Society TB Guideline, but also include a cholestatic pattern of DILI (with elevation of ALP) which is observed in

ſ	Trial	TB-DILI Trial	Protocol	1.2	date:	02-Aug-2022	Page 21 of 58
	name:		version:				

up to 17% of ATT DILI cases. Case definitions for DILI in patients who have elevations of ALT or ALP  $\leq$  1.5 x ULN prior to the onset of ATT would be the same as those with normal ALT or ALP at the onset of ATT. In patients with ALT or ALP elevation  $\geq$  1.5 x ULN prior to ATT, it is important to distinguish natural fluctuations in ALT/ALP levels from DILI. For the TB-DILI trial, the following will apply:

in patients with ALT or ALP elevations  $\geq$ 1.5 x ULN prior to ATT, DILI will be defined as

- ALT  $\geq$ 3 x upper limit of baseline levels or
- ≥ 300 U/L or
- ALP  $\ge$  2 x upper limit of baseline,

irrespective of bilirubin elevation or hepatitis symptoms.

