# Definition of Recovery from DILI:

- 1) in those who had normal baseline LFTs return of liver enzymes to less than 2 x ULN ALT plus bilirubin in normal range,
- 2) in those who had elevated baseline LFTs either i) return of liver enzymes to less than 2X ULN ALT plus bilirubin in normal range or, ii) return to baseline levels, whichever is the greater; *PLUS* resolution of signs and symptoms of hepatotoxicity after withdrawal of ATT drugs (criteria based on the American Thoracic Society TB Guideline and NICE TB Guideline).

**Hepatic Adjudication Panel.** Liver enzyme elevation in isolation is not a sufficient criterion to confirm a diagnosis of DILI. Other factors to consider are i) temporal association of ATT with elevation of liver tests, and ii) exclusion of alternative explanations.

A blinded Hepatic Adjudication Panel will review all relevant data relating to possible DILI episodes. The panel will judge the probability of ATT-related DILI and DILI severity according to defined criteria. Differences will be resolved by consensus, with the option of co-opting a third panel member as needed.

ſ	Trial	TB-DILI Trial	Protocol	1.2	date:	02-Aug-2022	Page 22 of 58
	name:		version:				

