# 14.2.2. Planned Final Analyses

The analysis and reporting of the trial will be in accordance with CONSORT guidelines, with the primary comparative analyses being conducted according to randomised allocation with due emphasis on confidence intervals for between-arm comparisons. A full statistical analysis plan will be developed prior to unblinding the trial statistician.

Descriptive statistics of demographic and clinical measures will be used to assess balance between the randomised arms at baseline, but no formal statistical comparisons will be made. Continuous variables will be summarised in terms of the mean, standard deviation, median, lower and upper quartiles, minimum, maximum and number of observations. Categorical variables will be summarised in terms of frequency counts and percentages.

The primary comparative analysis will employ generalised linear mixed effects regression modelling to compare the proportion with a DILI recurrence at 12 months in each group, adjusting for minimisation variables. The comparison will be presented as both an absolute (risk difference) and relative (risk ratio) effect, along with 95% confidence intervals. Secondary outcomes will be analysed using appropriate mixed effects regression models dependent on data type (binary, continuous, survival etc.), adjusting for minimisation variables.

The primary approach to between-group comparative analyses will be by intention-to-treat, that is including all participants according to randomised allocation regardless of adherence. Participants

Trial	TB-DILI Trial	Protocol	1.2	date:	02-Aug-2022	Page 47 of 58
name:		version:				

who complete treatment without DILI recurrence will be assumed to not meet the primary outcome (i.e., no recurrence of DILI), unless there is evidence to the contrary. All available evidence indicates the risk of ATT-DILI following cessation of drugs can be assumed as zero (no published reports known). Using this approach, we expect there to be very little missing primary outcome data but will use multiple imputation if required so that all randomised participants may be included in the primary analysis.

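### The primary outcome can be met by liver enzymes alone, but liver tests are optional in this open-label trial, so detection of symptom-free recurrence can differ by arm, in an uncertain direction

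*Protocol*

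**What the plan says.** The primary outcome (Protocol 2.2.1) is "DILI recurrence within 12 months following randomisation". The case definition in section 4.2 can be met by one laboratory criterion alone, for example ">5-fold elevation above ULN of alanine aminotransferase (ALT"; an ALP criterion without symptoms is also listed. For participants with raised enzymes before treatment, the thresholds apply regardless of symptoms or bilirubin. Section 1.1 agrees that silent rises count: "very high levels of liver enzymes (>5x upper limit of normal) in the absence of symptoms are thought to represent early DILI episodes".

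Testing is left open. The LFT row of Figure 2 (section 8.1) is labelled "LFT (suggested not mandated". Section 4.2 adds: "Participating sites will be encouraged to adopt a preferred monitoring plan with flexibility for local practice variations across hospitals". On data capture it says: "Sites will be requested to upload all LFTs performed onto the eCRF". In Figure 2 as printed, this row stands in the control-arm block; the intervention-arm assessments list only the EQ-5D-5L.

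Participants and site staff are unblinded (section 6.3). The safeguard is in section 4: "A blinded Hepatic Adjudication Panel will review all relevant data relating to possible DILI episodes". For the analysis, section 14.2.2 says that participants "who complete treatment without DILI recurrence will be assumed to not meet the primary outcome", with an exception where contrary evidence exists. Its stated reason is that the risk after the drugs are stopped can be taken as zero.

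**The concern.** A symptom-free recurrence enters the data only if blood is drawn while enzymes are raised and the result is recognised. The protocol fixes neither the frequency of testing nor a minimum amount of it, and those who decide on testing know the arm. The completer rule then turns an event nobody looked for into a non-event. Such participants are not missing, so the multiple imputation planned in section 14.2.2 never reaches them. The zero-risk argument covers the time after treatment, not unmeasured events during it.

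The blinded panel protects the classification of episodes put before it, but not their detection. At stake is the primary comparison: unequal detection biases the risk difference and risk ratio, and equal under-detection costs power. Analysis cannot restore tests that were never done.

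**Working it through.** **Inputs from the protocol (section 14.1.1).** Recurrence 10% v 1.5%; two-sided 5%; pooled-variance Z-test; 157 per arm analysed out of 175 recruited.

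**The plan's own figure.** With mean rate p̄ = (p1 + p2)/2 = 0.0575,

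n = [1.960·√(2p̄(1−p̄)) + 1.282·√(p1(1−p1) + p2(1−p2))]² / (p1−p2)² = 155.5, so 156 per arm, and 174 after 10% loss. The protocol states 157 and 175. Power at 157 per arm is 90.3%. The design reproduces. Expected events are 157 × 0.10 = 15.7 and 157 × 0.015 = 2.4, so a few missed events matter.

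**Unequal detection with no true difference.** The protocol gives no detection shares, so these are assumptions: true recurrence 10% in both arms; a share *a* of recurrences is symptom-free; control detects all events; intervention detects all symptomatic and half of the symptom-free ones. The observed intervention rate is then 10% × (1 − 0.5a).

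The rejection probability is Φ[(d − 1.960·SE0)/SE1] + Φ[(−d − 1.960·SE0)/SE1], with d the observed difference, SE0 = √(2p̄(1−p̄)/157) and SE1 = √([p1(1−p1) + p2(1−p2)]/157).

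| a | observed rates | d | SE0 | SE1 | P(two-sided p < 0.05) |
|---|---|---|---|---|---|
| 30% | 10% v 8.5% | 0.015 | 0.0327 | 0.0327 | 0.0666 + 0.0078 = 7.4% |
| 50% | 10% v 7.5% | 0.025 | 0.0319 | 0.0319 | 0.1196 + 0.0030 = 12.3% |
| 70% | 10% v 6.5% | 0.035 | 0.0311 | 0.0310 | 0.2020 + 0.0010 = 20.3% |

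With equal detection the same formula returns 5.0%.

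**The opposite direction.** If control alone detects 80% of events at the design rates (observed 8% v 1.5%), power falls from 90.3% to 77.5%.

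**Equal under-detection.** If both arms miss 30% (7% v 1.05%), d = 0.0595, SE0 = 0.0222, SE1 = 0.0219 and power is Φ(0.73) = 76.8%.

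**Whose row is the LFT row?** It carries marks from day 0 to W32. Figure 2 puts the control end-of-treatment assessment at W25, so the W32 mark makes sense only for the intervention arm. Appendix A speaks of a single LFT schedule for the main trial, without distinguishing arms. Both suggest that the row was meant for both arms.

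**The case against.** Flexible monitoring is a declared choice in a pragmatic trial, and section 4.2 gives its reason: the national guideline sets no specific plan. The schedule suggests twelve routine test points in people who have just had DILI, so the realistic worry is uneven frequency rather than no testing at all. Section 1.1 holds that silent ALT rises above five times the limit, if exposure continues, go on to symptoms; on that account many missed ALT events would surface later. Sites are asked to upload every test performed and data are checked centrally, so threshold crossings could be picked up without the site's suspicion. All of this stands, and it limits the size of the problem. But none of it sets a minimum of testing or states that a threshold-crossing result must go to the panel.

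Two stronger readings do not stand. A reader might infer from Figure 2 that only the control arm is to be tested. The W32 mark and Appendix A speak against this, and the figure's intervention block is damaged in the text available, so the original needs checking. A reader might also infer that the bias must favour the intervention. No section says that the pyrazinamide arm will be tested more, and nine months of treatment against six (section 1.2.3) gives more occasions for testing in the intervention arm.

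**Conclusion.** The concern holds as a risk of unequal ascertainment of the primary outcome, in an uncertain direction. It rests on four features of the protocol together: an outcome that enzymes alone can satisfy, testing that is optional and locally variable, unblinded sites, and a completer rule with no testing condition. The false-positive rates of 7.4% to 20.3% illustrate what assumed detection shares would do; they are not predictions. They are upper-end figures because they treat missed silent events as missed for good. The fall in power to 77% is a separate effect that needs no difference between arms, only that 30% of events go undetected in both. The sample-size arithmetic itself is sound. The placement of the LFT row in Figure 2 is an inconsistency to be reconciled, not evidence of planned unequal testing.

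**What to change.** 1. Reconcile Figure 2 with Appendix A so that one LFT schedule for outcome ascertainment, at the time points already listed, is shown for both arms through each arm's end of treatment. The intervention arm's end-of-treatment assessment is W33 in Figure 2 but W37 in section 9.1.4, so that must be settled too.
2. Have the database send every uploaded LFT that crosses a DILI threshold to the blinded panel, whatever the site suspects.
3. Report the number and timing of LFTs by arm. Add a sensitivity analysis in which completers with no or too few on-treatment LFTs, by a limit set before unblinding, are treated as missing rather than event-free.

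Whether LFTs should be mandated as clinical monitoring is for the sponsor to decide; the steps above do not depend on it. The cost is a corrected figure, a database rule, and some extra panel and analysis work. The sample size does not change.
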